2. Determine if active tDCS augments cortical excitability after gait training. Cortical excitability will be defined by a cortical recruitment curve, a primary outcome measure, derived from plots of motor evoked potentials (MEPs) recorded from the ipsilesional TA muscle. MEPs are elicited by single pulse transcranial magnetic stimulation (TMS) delivered at increasing intensity over motor cortex. Changes in the slope of the recruitment curve signal change in cortical excitability. Difference scores from baseline will be compared between active and sham groups to determine if tDCS augments cortical excitability after FESAGT. A repeat fMRI will be performed to assess change in cortical excitability after gait training.
3. Determine if active tDCS augments physical function and social wellbeing. The Stroke Impact Scale-16 (SIS-16), a primary outcome measure, will be used to assess ADL/IADL, mobility, and social and occupational engagement at baseline and post treatment assessments. Difference scores from baseline will be compared between active and sham groups to determine if tDCS augments physical function and social well-being.

Exploratory Aim

Identify patient characteristics that predict response to treatment. Patients will be classified empirically based on their response to treatments. Regression analyses will examine whether and how initial impairment, functional level, and cortical excitability predict a treatment response.

Study Interventions

tDCS and gait training will be conducted at UCA three times a week for 4 consecutive weeks

Version 10 Revised 11/21/2014

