Stroke subjects will be recruited via advertisement and from participants in past stroke studies who indicated a willingness to be contacted for additional studies. We will recruit participants > 3 months post unilateral, stroke to minimize confounding effects of spontaneous recovery. Subjects who participated in previous versions of the study will be re-contacted if they indicated they were willing to be contacted for additional studies.

Version 10 Revised 11/21/2014

Title: Using tDCS to Jump Start Gait Training and in Chronic Stroke Patients

PI: [name]

If they are willing to participate in the revised study they will be re-consented and re-enrolled under the new protocol.

Screening Procedures

All screening procedure will be conducted at either UAMS or UCA

For women of childbearing years a free pregnancy testing (urine dip stick test) will be required.

Administration of NIH Stroke Scale: administered and scored by study personnel who interview the participant. Severe language communication difficulties would preclude participation.

Administration of modified Rankin Scale: administered and scored by study personnel who interview the participant.

Administration of TMS Adult Safety Screening (TASS, determine study eligibility): by study personnel.

Medical records will be reviewed to evaluate participant's study acceptability and to obtain clinical studies including neuroradiological imaging studies.

MRI procedures

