Post-Intervention Procedures (Study Weeks 5(± 5 days) and 8 (± 10 days) :

During Study Weeks 1-5, and 8 Gait assessment (details provided in **Outcome Measures**) and the Stroke impact Scale 16 will be performed at UCA. During Study Weeks 5 and 8 TMS will be performed at UAMS and participants will complete a repeat fMRI scan. Details of TMS procedure used to establish recruitment curves are located in the Outcome Measures.

Reduction of Study Bias:

[name] will supervise delivery of interventions, and so, he will not be blinded to tDCS condition; however, Drs. [name] and [name] who collect and analyze data will be blinded to condition.

Study Locations:

tDCS, gait training, SIS-16, and the assessments of gait will take place in the Motion Analysis Laboratory at UCA; motor evoked potentials and recruitment curves developed from TMS are measured in the TMS and Human Electrophysiology core facilities at UAMS. Subject burden is reduced by requiring only four trips to UAMS over two - three months. (Subjects are informed that scheduling conflicts could result in an extra visit.) UAMS will be the IRB of record and Sponsor of the IDE.

Study Schedule

	Screening	Baseline	Study Weeks 1 -4 ^b	Study Week 5	Study Week 8
Consent	X				
Screening	X				
NIH Stroke Scale	X				
Modified Rankin Scale	X				
TASS	X				
Medical Record Review	X				
MRI	X			X	
Pregnancy Assessment	X				
Randomization	X				
Assessments					
Gait assessments		X	X	X	X
RC & SIS		X		X	X
Interventions					
tDCS			X		
Sham tDCS			X		
Gait training			X		

Definitions: TASS= Transcranial Magnetic Stimulation Adult Safety Screen, MRI=magnetic resonance imaging, RC & SIS-16=recruitment curve established using transcranial magnetic stimulation (TMS) and Stroke Impact Scale . ^bThree times a week for four weeks participants will receive active or sham tDCS and gait training interventions at UCA for a total of 12 treatment periods.

Study Population

Up to 100 stroke patients will be enrolled to obtain 88 who meet entry criteria and complete study procedures (i.e., 44 participants in each of the active or sham tDCS groups). Attrition, estimated at about 15%, will be handled by replacement.

Participants will be ≥21 years old to better represent the general stroke population. All participants will complete the NIH Stroke Scale, have evidence of gait impairment, and will be able to fully and safely participate in treatment.

Inclusion Criteria

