Exploratory Aim. We will classify patients as “likely responsive” and “likely unresponsive” to tDCS based on the magnitude of difference scores and compare them to determined patient characteristics that predict a treatment response. Predictors for 88 subjects include 1) NIH Stroke Scale score, 2) initial levels of impairment, 3) initial MT of the contralateral TA muscle (and recruitment curve parameters from the ipsilateral TA muscle), 4) initial SIS-16 total and subscale scores, 5) stroke laterality, and 6) modified Rankin Scale scores. A series of regression analyses will be conducted to reduce the overall number of predictors and to build an initial model, which assess the predictive value or weight of remaining variables, and to cross-validate predictors. To determine which stroke related variables are associated with a response to treatment, brain lesions will be mapped onto templates and analyzed using lesion subtraction techniques with the public domain MRIcro and MRIcron software programs (see Core B). Lesion subtraction will identify the lesion sites that are common to treatment responders and not common to nonresponders.

Ethical Considerations

This study will be conducted in accordance with all applicable government regulations and University of Arkansas for Medical Sciences research policies and procedures. This protocol and any amendments will be submitted and approved by the UAMS Institutional Review Board (IRB) to conduct the study.

The PI or designated staff will discuss the informed consent form with the subject volunteer. The consent process will take place in a quiet and private room. Subjects may take as much time as needed to make a decision about their trial participation and may take the document home if desired. The person obtaining consent will thoroughly explain each element of the document and outline the risks and benefits, alternate treatment(s), and follow-up requirements of the study. Participation privacy will be maintained and questions regarding participation will be answered. No coercion or undue influence will be used in the consent process. No research related procedures will be performed prior to obtaining informed consent. All signatures and dates will be obtained. A copy of the signed consent will be given to the participant. The informed consent process will be documented in each subject’s research record.

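### Exploratory Aim: untested lesion subtraction is said to identify responder sites, continuous change is split into two classes, and predictor selection is not tied to the cross-validation

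*Combined protocol and SAP*

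**What the plan says.** The protocol lists the aim as exploratory: "Identify patient characteristics that predict response to treatment" (Exploratory Aim, under Specific Aims). The Exploratory Aim paragraph of the Data Analysis section then sets out three steps.

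- **Outcome.** Patients are put into a responsive and an unresponsive class "based on the magnitude of difference scores". The paragraph does not name the outcome measure or the cut-off.
- **Regression.** "Predictors for 88 subjects include 1) NIH Stroke Scale score, 2) initial levels of impairment", followed by "initial MT of the contralateral TA muscle (and recruitment curve parameters from the ipsilateral TA muscle"), SIS-16 total and subscale scores, stroke laterality and modified Rankin score. The plan continues: "A series of regression analyses will be conducted to reduce the overall number of predictors and to build an initial model". Assessing the weight of the remaining variables and cross-validating the predictors come next in the same sentence. No selection method, significance level or fold scheme is given.
- **Lesions.** Lesions are mapped to templates and subtracted: "Lesion subtraction will identify the lesion sites that are common to treatment responders and not common to nonresponders". No test, threshold or multiplicity control is stated. The text points to a Core B, which is not among the documents.

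**The concern.** The aim is meant to say who benefits from tDCS, and the background section presents matching patients to therapies as one reason for the study. Three features work against a reliable answer.

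First, a subtraction map is a descriptive difference of two proportions at each location. It will show locations with a responder excess whether or not lesion site matters, so it cannot by itself identify anything.

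Second, cutting a continuous difference score into two classes discards information that 88 patients can ill spare.

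Third, cross-validation is honest only if every step that used the outcome, including the choice of predictors, is repeated without the held-out patients. The plan lists reduction before cross-validation and does not say that the reduction is repeated. If it is done once on everyone, a model built on noise will carry the label of having been cross-validated.

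**Working it through.** The plan states no error rate, power or performance figure for this aim, so there is nothing of its own to reproduce.

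**Inputs from the documents.** The model covers 88 patients, with "44 participants in each of the active or sham tDCS groups". The six predictor items expand to at least 12 variables: NIH Stroke Scale 1, impairment 1, motor threshold 1, recruitment-curve parameters 3 (threshold, slope and MEPmax, Outcome Measures, Study Aim 2), SIS-16 total plus 3 domains 4 (Study Aim 3), laterality 1, Rankin 1.

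**Assumed, because not given.** 6, 14 or 20 candidates; correlation between them 0 or 0.3; removal at 0.05 or 0.10; a 50:50 responder split; 20 or 100 independent lesion regions; lesion prevalence 10, 20 or 30%.

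**1. Lesion subtraction with equal true lesion rates** (44 responders, 44 nonresponders, 4,000 runs per row). In every run at least one region was commoner in responders.

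| Prevalence | Regions | Median largest responder excess | Runs with an excess of 20 points or more |
|---|---|---|---|
| 10% | 20 | 11.4 points | 2.5% |
| 10% | 100 | 15.9 | 12.5% |
| 20% | 20 | 15.9 | 20.0% |
| 20% | 100 | 20.5 | 69.3% |
| 30% | 20 | 18.2 | 38.5% |
| 30% | 100 | 25.0 | 91.1% |

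Hand check for one location at 20% prevalence: the difference in lesion counts has SD √(2 × 44 × 0.2 × 0.8) = 3.75. An excess of 10 points is 4.4 patients, so at least 5. With continuity correction, P(Z ≥ 4.5/3.75) = 0.115. An excess of 20 points is 8.8 patients, so at least 9, and P(Z ≥ 8.5/3.75) = 0.012. A large excess is therefore uncommon at any one location. It becomes common when the largest of many is read off the map.

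**2. Splitting the outcome.** For a normal difference score, a median split multiplies its correlation with a predictor by √(2/π) = 0.798. Taking r = 0.3 as an example, n = 88 and two-sided α = 0.05, with the Fisher transformation:

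- Continuous: atanh(0.300) × √85 = 2.85; power = Φ(2.85 − 1.96) = 0.81.
- Median split: 0.3 × 0.798 = 0.239; atanh(0.239) × √85 = 2.25; power = Φ(2.25 − 1.96) = 0.61. A simulation gave 0.62.

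The equivalent sample size is 88 × 2/π = 56.

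**3. Selection and cross-validation on pure noise.** For independent candidates, the chance that at least one passes is 1 − (1 − α)^p. At 0.05 this is 0.27, 0.51 and 0.64 for p = 6, 14 and 20. At 0.10 it is 0.47, 0.77 and 0.88. For the 12 variables counted above it is 0.46 and 0.72.

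Backward elimination, n = 88, 10-fold cross-validation, 300 runs per row; AUCs are means over runs that kept at least one predictor:

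| Candidates | Correlation | α | Any kept | AUC, selection outside folds | AUC, selection inside folds |
|---|---|---|---|---|---|
| 6 | 0 | 0.05 | 0.26 | 0.617 | 0.520 |
| 6 | 0.3 | 0.05 | 0.32 | 0.613 | 0.510 |
| 6 | 0.3 | 0.10 | 0.52 | 0.600 | 0.503 |
| 14 | 0 | 0.05 | 0.49 | 0.623 | 0.496 |
| 14 | 0.3 | 0.05 | 0.53 | 0.631 | 0.495 |
| 14 | 0.3 | 0.10 | 0.81 | 0.615 | 0.483 |
| 20 | 0 | 0.05 | 0.68 | 0.639 | 0.494 |
| 20 | 0.3 | 0.05 | 0.66 | 0.633 | 0.491 |
| 20 | 0.3 | 0.10 | 0.89 | 0.639 | 0.482 |

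The conditioning matters. Counting runs with no predictor as 0.50, the outside-fold mean is 0.26 × 0.617 + 0.74 × 0.50 = 0.53 in the first row and 0.89 × 0.639 + 0.11 × 0.50 = 0.62 in the last. If only the 44 active patients were modelled, the conditional means were 0.65 to 0.71 outside and 0.47 to 0.51 inside.

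**The case against.** The strongest reply is that the plan is unspecific rather than wrong. Its sentence on the regressions lists purposes. A reader might infer that predictors are cut once on all 88 patients and only then cross-validated, but the text does not say so: the figure of 88 gives the sample, and selection repeated within folds fits the same words. That stands. The optimism in the third step is conditional on how the work is done. The plan also promises no AUC, so that measure is only a yardstick.

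A reader might also conclude that the regressions are bound to produce predictors from noise. They are not: 26 to 89% of null runs kept one, depending on settings that the plan leaves open.

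On lesions, Core B may describe a test. One can say only that none is stated here, and the documents should stand on their own.

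Two further readings go too far. The Recruitment section sets entry at more than 3 months after stroke "to minimize confounding effects of spontaneous recovery". That handles early recovery through eligibility. It does not make time since stroke the main confounder of change, and the predictor list is worded as inclusive, so its absence there proves little. Nor do the documents give the SIS-16 scoring that would be needed to call the total and its subscales exactly collinear.

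Finally, the aim is exploratory and the model is called an initial one. That limits the consequence. It does not make a subtraction map into a finding.

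**Conclusion.** The point holds for three features of the Exploratory Aim, in descending order of certainty.

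- **Lesion subtraction** is credited with identifying sites, without a stated test. With no true difference, a responder-excess region appeared in every simulated run. The median largest excess was 11 to 18 points with 20 regions and 16 to 25 with 100, assuming independent regions and a 44/44 split.
- **The two-class outcome** is stated in the plan and costs power: about 0.81 to 0.61 at r = 0.3, assuming a median split of a normal score.
- **Cross-validation** is left open. If selection stays outside the folds, noise gives a mean AUC of 0.60 to 0.64 against 0.48 to 0.52 when nested, among runs that keep a predictor and under the assumed selection settings.

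The documents do not support saying that the plan prescribes selection outside the folds, or that noise predictors are certain. Aims 1 to 3 and the sample size are untouched.

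**What to change.** - **Lesions.** Replace subtraction with a voxel-wise or region-wise test with permutation-based error control. Otherwise label the map descriptive and remove the statement that it identifies sites. If Core B already specifies a test, write it into the plan.
- **Outcome.** Model the continuous difference score and name which one. If responder classes are kept for display, fix the cut-off in advance.
- **Prediction model.** State the candidate list, the selection rule and the fold scheme. Repeat the whole selection process within every fold or bootstrap sample, and report only that performance. Nesting removes the optimism in the performance estimate but does not stop noise variables from being selected, so the chosen predictors should still be described as hypotheses.

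This needs no new patients, visits or data. The cost is a little more analysis work and a lower reported predictive accuracy.

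### The exploratory lesion subtraction, as described, makes no allowance for lesion volume, so if response is related to lesion size the map mixes size with site; a cheap addition would show this.

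*Combined protocol and SAP*

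**What the plan says.** The Exploratory Aim, under Hypothesis and Specific Aims, promises that "Regression analyses will examine whether and how initial impairment, functional level, and cortical excitability predict a treatment response". Lesion size is not mentioned there.

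The matching paragraph in Data Analysis classifies patients as likely responsive or unresponsive "based on the magnitude of difference scores", without a cut-off. It then names six predictor groups, opening with "Predictors for 88 subjects include 1) NIH Stroke Scale score, 2) initial levels of impairment". The other four are TMS measures (motor threshold and the recruitment curve), SIS-16 results, the side of the stroke, and the Rankin score. Lesion volume is not one of them, but the list is introduced by a verb that leaves it open.

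For imaging, the same paragraph says that "brain lesions will be mapped onto templates and analyzed using lesion subtraction techniques". The output it promises is one-sided: "Lesion subtraction will identify the lesion sites that are common to treatment responders and not common to nonresponders". It names no covariate, size matching, stratification, test or threshold. It cites Core B in connection with the lesion method and software; that document is not among those supplied.

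**The concern.** A larger lesion is more likely to cover any given region. If response depends on lesion size, responders and nonresponders will differ in how often a region is damaged, even where damage to that region has no effect of its own. A subtraction map can return only locations, so it cannot show that the difference came from size. This is confounding rather than chance, so a significance test or a multiplicity correction of the map would not remove it.

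The direction decides the harm, because the planned output is one-sided. If responders have the larger lesions, false sites are added to the responder list. If nonresponders have them, overlap in responders is pushed down everywhere and a true responder site can be missed. What is at stake is the reading of an exploratory map, not a primary comparison.

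**Working it through.** **What the documents allow.** The plan gives no figure for lesion size or for its relation to response, so there is nothing of its own to reproduce. A check of all the supplied text for lesion size, volume or extent found no mention. That volume will be available is an inference: a lesion drawn on a template has a voxel count.

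**Assumed inputs for the illustration.** Only the sample size of 88 comes from the protocol (Study Population; Data Analysis).
- Half the patients have large lesions and half small.
- Any region is hit in 40% of large and 15% of small lesions.
- Response depends on size only; no region has an effect. Overall response is 50%, so about 44 patients fall in each group.
- A region is flagged when the lesion rate in responders exceeds that in nonresponders by at least 20 percentage points. The plan gives no threshold, so this is my reading of common to one group and not to the other.

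**Lesion rate by group.** With response probability a for large lesions and b for small (a + b = 1):
- rate in responders = (0.5·a·0.40 + 0.5·b·0.15)/0.5 = 0.40a + 0.15b
- rate in nonresponders = 0.40(1−a) + 0.15(1−b)

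**Chance that a region is flagged.** With D the difference in rates, SE = √[(p₁(1−p₁) + p₂(1−p₂))/44], and P(flag) ≈ 1 − Φ((0.20 − D)/SE).

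| Response, large v small | Responders | Nonresponders | D | SE | P(flag), normal approximation | P(flag), simulation |
|---|---|---|---|---|---|---|
| 50% v 50% (no size effect) | 27.5% | 27.5% | 0 | 0.095 | 1.8% | 1.9% |
| 60% v 40% | 30.0% | 25.0% | +5 points | 0.095 | 5.7% | 6.0% |
| 70% v 30% | 32.5% | 22.5% | +10 points | 0.095 | 14.5% | 15.1% |
| 30% v 70% | 22.5% | 32.5% | −10 points | 0.095 | 0.1% | 0.1% |

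The simulation used 20 regions, 88 patients and 20,000 runs per row. In the 70% v 30% row, comparing responders with nonresponders within size class and pooling brought the mean difference back to zero and the share of regions favouring responders back to 50%.

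**A second model.** Lesions were simulated as spheres of varying volume on a 20×20×20 template, with 88 patients, responders taken as the upper half of the difference score, and no site effect. The mean number of voxels with a responder excess of at least 20 points was 11 when volume and response were uncorrelated. It was 63 at a correlation of +0.3 and 170 at +0.5, but only 0.6 at −0.3 and 0.06 at −0.5. The pattern does not depend on the simple two-class model.

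**The case against.** **Absence is not proved.** Core B may deal with lesion size, and the predictor list is open. This stands: one can say only that the supplied text is silent. An extra predictor in the regression would still not bring size into the subtraction.

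**A reader might infer that any size effect will be reported as a site effect.** The one-sided rule does not support that. If larger lesions go with poorer response, the responder list holds fewer false sites than chance alone gives (0.1% of regions against about 2%). The harm then is concealment, not false discovery.

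**A reader might infer that most sites would look common to responders.** In the 70% v 30% scenario about 85% of regions do lean towards responders, but that counts any difference above zero. Only about 15% reach 20 points. On a stricter reading (lesioned in at least half of responders and under half of nonresponders) it is about 1%, against 0.1% with no size effect.

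**A reader might infer that patients will be wrongly selected for treatment.** The documents nowhere say that the map will be used for selection. The stated aim is to identify characteristics that predict response. Selection advice would in any case be limited by running the predictors on all 88 patients, sham included, which lesion volume would not cure.

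**Adjustment is a trade-off.** Where site and volume are correlated, adjusting can remove part of a true site effect. This stands, and is why the planned map should be kept rather than replaced.

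**Conclusion.** The point holds conditionally. On the supplied text, lesion volume is neither a named predictor nor allowed for in the subtraction, so this analysis could not tell an effect of size from an effect of site. If responders have larger lesions, false responder sites rise from about 2% of regions to about 6% or 15% in the scenarios shown; if nonresponders do, the responder list nearly empties and true sites may be hidden.

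These sizes rest on assumed lesion rates, response rates and a 20-point threshold. The documents do not show that lesion size is related to response in this population, and do not show in which direction. The aim is exploratory and no primary comparison changes. Severity is low: a cheap improvement.

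**What to change.** Add to the Exploratory Aim paragraph in Data Analysis:

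*Lesion volume, taken as the voxel count of the mapped lesion, is a candidate predictor of response and will be summarised for responders and nonresponders. A comparison of lesion sites adjusted for lesion volume will be presented beside the subtraction map. The subtraction map is descriptive.*

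If Core B already handles lesion size, a sentence saying how is enough.

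The cost is one derived number per patient from maps already planned, with no extra scan or visit, plus a modest amount of exploratory analysis. The adjusted comparison needs a short statement of the regions used, the fewest lesioned patients for a region to be analysed, and how multiple regions are handled. Because adjustment may weaken a true site effect where site and volume are correlated, both versions should be shown and neither treated as confirmatory.
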